### Newborn screening

Current newborn screening

Newborn screening can be carried out using a variety of approaches including newborn physical examination, newborn hearing screening and newborn blood spot testing.

Since the 1960s screening newborns for treatable disorders by heel prick blood spot testing has proven effective in preventing or dramatically ameliorating the burden of disease for these conditions. Newborn blood spot screening has been deployed successfully worldwide and the rapid development of new technologies has expanded the disorders tested.

The number of conditions tested for varies in different countries. In Italy, 40 conditions are looked for. In the United States, the recommended universal screening panel covers 35 conditions. In Australia and New Zealand 25 conditions are screened for and in Germany 19. The UK Newborn Blood Spot Test currently tests for nine conditions:

- sickle cell disorder
- cystic fibrosis
- congenital hypothyroidism

- phenylketonuria
- medium-chain acyl-CoA dehydrogenase deficiency
- maple syrup urine disease
- glutaric aciduria type 1
- homocystinuria and
- isovaleric academia

In the UK, a pilot is ongoing to evaluate the addition of severe combined immune deficiency (SCID) screening. Screening for tyrosinaemia has recently been recommended for inclusion by the UK National Screening Committee. Alongside the Newborn Blood Spot Test sit other newborn screening programmes such as hearing screening and newborn physical examination.

Performance of newborn screening programmes including false positive rates

A range of parameters are closely monitored for newborn screening including overall uptake as well as performance metrics such as sensitivity, specificity and observed true and false positive rates. The balance of these different parameters depends partly on the nature of the condition and partly on performance of test(s). The approach chosen also depends on the cost, availability and nature of confirmatory testing and balances the clinical utility of the finding and the impact of the condition if not detected early or before symptoms appear and the negative impacts of false positive findings on the child, the family and the health system.

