## The secondary outcomes are:

- To determine the feasibility and acceptability of genomic newborn screening in the NHS utilising mixed-method approaches to assess study implementation.
- To determine the cost effectiveness of genomic newborn screening compared to standard of care alone, supported by a health economic model developed to support the programme.
- To determine whether families' and stakeholders' experiences and attitudes are supportive of the adoption of genomic newborn screening.
- To determine any differential areas of positive or negative impact of genomic newborn screening related to indices of diversity including ethnicity and socio-economic deprivation.

The exploration of the research questions and realisation of these outcomes - and the assessment of feasibility and acceptability in particular - requires an extensive, multidisciplinary project evaluation drawing on a range of specific expertise in newborn screening and implementation and behavioural science. Therefore, as well as external experts on economic modelling, Genomics England will engage an Evaluation Partner to undertake this work with us.

We will co-create an Evaluation Protocol with our Evaluation Partner with external advice including from the UK National Screening Committee. The Evaluation Protocol will govern and set out the work and analytical plans in detail including any additional participant-facing materials related to this work e.g., on interviews and questionnaires with participating families.

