Where there is a known history of a genetic or other condition, site study teams will be encouraged to ensure that standard of care processes are not disrupted and that referrals are made to relevant specialists as appropriate.

Study teams will be asked to record locally any information on numbers of participants approached vs consented. We will receive aggregated data on consent numbers as a numerator of those approached in order to determine the uptake rate of the study.

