## Economic modelling

GEL is developing an economic model internally for the health economic evaluation. The initial proposals for the model were produced through a collaboration between GEL and external experts, with the model itself developed by an external economic modelling team. GEL continues to liaise with the NSC and other expert teams on the model. We include a description of the model below, noting that it will be iterated and populated as data from the Generation Study and other studies are generated and responding to ongoing expert input and best practice.

The model aims to estimate the costs and benefits of genomic newborn screening alongside current newborn bloodspot screening. The model includes a control arm, current blood-spot test, as well as an intervention arm for the addition of genomic newborn screening. Consent rates for both screening tests are incorporated, resulting in a subset of babies receiving neither screening test.

The model takes a clustering approach, grouping conditions with similar clinical characteristics, clinical pathways and natural histories together. In total the model currently contains six clusters of conditions that have similar characteristics each of which is represented by around ten conditions. This subset of ~60 conditions, representing the 200+ conditions that will be screened for by WGS, was chosen based on prevalence, data availability, and also clinical importance. Within each cluster, condition-specific inputs are obtained for costs, utilities, and mortality rates, and a weighted cluster average is then calculated for each variable based on the relative prevalence of the condition within the cluster. The model is run individually for each of the six clusters and then aggregated to reach a population-level estimate, based on the relative prevalence of each cluster within the overall population. This allows for cost-effectiveness to be estimated both for individual clusters and for the overall group of conditions.

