The model is structured in two phases. The first phase, a decision tree (shown below), considers the initial screening process and is used to define distinct groups of patients based on the outcome of screening. In the second phase, these groups of patients then progress through one of three distinct Markov models, each simulating a specific post-screening pathway. For the first phase, a weekly-cycle length is used to capture the costs associated with the screening tests, the sequencing process, the interpretation of the screening results and finally the cost of confirmatory diagnostic tests. In the second phase, an annual cycle length is applied to all Markov models, with a half-cycle correction implemented, to capture all the relevant costs and benefits that babies accrue as they are followed for a lifetime time horizon.

The first Markov model (Model A) tracks babies affected with a genetic disease but who have not been detected via WGS or blood-spot (false negative), or who were not detected because of non-participation in the screening programme (i.e., parents declined screening). The second Markov model (Model B) tracks babies with a genetic disease detected by WGS or blood-spot (apparent true positive). The third Markov model (Model C) tracks unaffected babies, this includes babies with

negative WGS or blood-spot results, babies with positive WGS or blood-spot results which was subsequently disproved as negative by a diagnostic test (apparent false positive), and finally unscreened babies that did not participate in either screening program and never develop a genetic condition (unaffected). The model includes the positive predictive value (PPV) and negative predictive value (NPV) for both the blood-spot and WGS screening tests, which determine the number of false negatives and false positives in the population.

Apparent true + Markov Model B Condition(s) Clinical pathway & orthogonal testing Genomic Newbor Apparent false Markov Model C Screening + Genetic Condition Markov Model A No condition suspected result orthogonal testing Markov Model C Apparent true Markov Model B Condition(s) Clinical pathway & suspected resul orthogonal testing Standard of Care Apparent false + Newborn Blood-spor - Genetic Conditi Markov Model A No condition suspected result orthogonal testing Genetic Condition Markov Model C Genetic Conditio Markov Model A

Markov Model C

Figure 9- Decision tree for the draft health economic model

Genetic Condition

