Babies diagnosed with a genetic condition at birth, through either blood-spot or WGS will enter Markov model B in the "pre-symptomatic" health state, and those who subsequently receive treatment will continue through to the "asymptomatic-treatment" health state. From here, they will transition to one of three subsequent health states: "asymptomatic-complete response", "symptomatic-partial response", "symptomatic-treatment failure". The model also includes a "symptomatic-symptoms management" health state to reflect patients who will benefit from having a diagnosis, even without treatment initiation and those with uncertain condition status. Transition probabilities between health states are based on treatment efficacy rates, specific to each condition in the model. In addition, specific mortality rates are applied to each health state.

Babies diagnosed with a genetic condition at symptom onset, either due to false negative results or babies in the control arm who have conditions not screened for in the blood-spot test, will enter Markov model A. The health states in this model are similar to those in model B, except for the addition of a "symptomatic-diagnostic odyssey" health state, which captures the period of time between symptom-onset and receiving a diagnosis. In addition, in model A the "asymptomatic-treatment" state is replaced by the "symptomatic-treatment", since treatment will only begin after symptom onset and diagnosis. Despite the similarity in health-states between models A and B, the transition probabilities differ for some conditions due to reduced treatment efficacy when treatment

No Screen

is initiated at symptom onset rather than at birth. As with model B, specific mortality rates are applied to each health state.

Finally, Markov model C captures the progression of unaffected infants (false-positive, true-negative, and unaffected unscreened infants). Only two health states are considered for this model: "unaffected-well" and "death". For false positive patients, harms of a false diagnosis such as anxiety are captured within the first phase of the model, after a confirmatory negative test they are assumed to rejoin the "unaffected" population.

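### The economic model lets only the blood-spot test or WGS lead to pre-symptomatic care, so early diagnoses that standard of care would make through family history or at-risk surveillance are credited to WGS

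*Protocol*

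**What the plan says.** Section 5 states the secondary outcome as "To determine the cost effectiveness of genomic newborn screening compared to standard of care alone"; Appendix A poses the same question. Section 13 (Economic modelling) sets up the comparison: "The model includes a control arm, current blood-spot test, as well as an intervention arm for the addition of genomic newborn screening".

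Affected babies then have two destinations. Model B, the early pathway, "tracks babies with a genetic disease detected by WGS or blood-spot (apparent true positive"), and they start there as pre-symptomatic. Model A takes affected babies whom neither test detected, including those whose parents declined screening. For the control arm the text adds that "babies in the control arm who have conditions not screened for in the blood-spot test, will enter Markov model A". Model A has a diagnostic-odyssey state, and its treatment state is a symptomatic one, "since treatment will only begin after symptom onset and diagnosis". Transition probabilities are said to differ between the two models for some conditions.

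Elsewhere the protocol describes routine care more widely. Section 7 deals with families "Where there is a known history of a genetic or other condition": sites are encouraged to leave standard processes undisturbed and to make specialist referrals. The risk table in Section 17 names referral on medical or family history as part of routine care. Section 3 (Treatments) gives eye surveillance of children at risk of retinoblastoma as an existing intervention, and Section 4 expects hereditary retinoblastoma to meet the principles for inclusion in the study.

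**The concern.** The question is asked against standard of care, while the control arm as built is the blood-spot test plus diagnosis after symptoms. A baby of an affected parent, or the sibling of an affected child, may be under specialist care before symptoms without any WGS. The model has no place for that baby in either arm.

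The omission works in one direction. In the control arm the baby is put on the late pathway; in the intervention arm, if WGS-detected, on the early one. The difference is booked as a benefit of WGS although standard of care would have produced it. Known family history is not an exclusion criterion in Section 6, so such babies can be in the study, and their findings can enter the model as live data. At stake are the incremental early diagnoses, QALYs and ICER that are meant to inform a policy decision.

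**Working it through.** The protocol states no figure on this point, so there is none to reproduce. The check is structural, followed by an illustration.

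**Placement of an affected baby whose condition is not on the blood spot**

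| Baby | Control arm | Intervention arm | Credited to WGS | Truly due to WGS |
|---|---|---|---|---|
| No other early route, WGS detects | A | B | yes | yes |
| No other early route, WGS misses | A | A | no | no |
| Other early route, WGS detects | A | B | yes | no |
| Other early route, WGS misses | A | A | no | no |

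Only the third row is wrong in the increment. The fourth row is misplaced in both arms and cancels.

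**Count of added early diagnoses.** Let s be the sensitivity of WGS and p the share of affected babies diagnosed pre-symptomatically by another route, independent of WGS detection.

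- Early under standard of care: p
- Early with WGS added: s + (1-s)p
- True increment: s + (1-s)p - p = s(1-p)
- Modelled increment: s
- Overstatement factor: s / [s(1-p)] = 1/(1-p), which does not depend on s

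**Illustration per 100,000 babies screened.** Section 6 (Sample size) gives an incidence of 1/572 for treatable disorders outside current newborn screening, and a sensitivity of 65%. Affected: 100,000/572 = 174.8. Modelled moves to early care: 174.8 × 0.65 = 113.6. The values of p are assumptions.

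| p (assumed) | True increment 113.6 × (1-p) | Over-credit | 1/(1-p) |
|---|---|---|---|
| 5% | 108.0 | 5.7 | 1.05 |
| 10% | 102.3 | 11.4 | 1.11 |
| 20% | 90.9 | 22.7 | 1.25 |

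**Effect on the ICER.** Let C be the screening cost per baby, i the incidence, and Δc and Δq the cost and QALY differences per baby moved from A to B, taken as constant; harms of false positives are left out.

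- True ICER = [C + i·s·(1-p)·Δc] / [i·s·(1-p)·Δq] = C/[i·s·(1-p)·Δq] + Δc/Δq
- Modelled ICER = C/[i·s·Δq] + Δc/Δq

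The first term is understated by the factor (1-p); the second does not change. If w is the share of the true ICER that comes from the first term, modelled/true = 1 - w·p. Where early treatment costs at least as much as late treatment, w is at most 1 and the ICER is too low by no more than p. The protocol gives no costs from which to compute w.

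**The case against.** The strongest reply is that this is a draft. Section 13 says the model will be iterated as data and expert input arrive, the caption of Figure 9 calls it a draft, and ages at diagnosis and treatment start in the comparator groups are already to be collected. That stands as a reason for moderate severity. It does not supply the missing path: the described sensitivity analysis varies existing inputs between bounds, the scenario example is the discount rate, and neither adds a route into Model B.

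The sentence on the control arm could also be read as covering only babies who happen to be diagnosed at symptom onset. The definitions of Models A and B rule this out, because affected babies not detected by either test have no other destination.

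The protocol also does not say how often family history leads to diagnosis before symptoms. That is correct; p may be small for many conditions.

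A reader might infer more than the text supports:

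- **Other programmes.** The protocol does say "Alongside the Newborn Blood Spot Test sit other newborn screening programmes such as hearing screening and newborn physical examination", but these find signs already present and are not shown to give pre-symptomatic diagnosis of study conditions. The SCID pilot and the spinal muscular atrophy study are presented as screening under evaluation, not as standard care.
- **Labelling.** The text of Figure 9 already carries standard of care beside the blood-spot branch, so the name of the arm is not the fault.
- **Late outcomes for all.** Where transition probabilities do not differ between A and B, misplacement costs only the diagnostic-odyssey and health-state differences.

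**Conclusion.** The point holds as a structural gap. As written, the model credits WGS with early diagnoses that standard of care would have made through family history, cascade testing or at-risk surveillance. The direction follows from the structure: for any p above zero, with a positive screening cost and a positive QALY gain, the ICER is too favourable.

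The size cannot be taken from the protocol. Added early diagnoses are overstated by 5%, 11% and 25% at assumed p of 5%, 10% and 20%, provided that p is independent of WGS detection and that WGS brings such babies no further gain in timing. If p differs between detected and missed babies, the value among the detected is the one that counts.

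It would be tempting to apply the same percentages to the ICER. That is not supported, because only the screening-cost term scales, and the QALY effect is smaller where the two models share transition probabilities. Nor can it be said that the cluster ICERs are distorted by known, unequal amounts: p may well vary by condition, but no cluster value is given. The primary outcome and the sample size are unaffected.

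**What to change.** Add to both arms of the decision tree a branch for pre-symptomatic diagnosis through family history, cascade testing or at-risk surveillance, leading to Model B, with a probability p specific to the condition or cluster. In the intervention arm the branch should also take such babies when WGS misses them, so that the two arms differ only by what WGS adds.

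Inform p from the rare conditions comparator group. Age at diagnosis and start of treatment are already planned there (Appendix A); also record the route to diagnosis and whether the child had symptoms at that point. Until those data exist, use expert values and vary p in the sensitivity analysis, including p = 0, which returns the present model. Hearing screening, physical examination, the SCID pilot and the spinal muscular atrophy study need no place in this branch, and the arm needs no new label.

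The cost is one more uncertain parameter per condition or cluster, two extra fields in the comparator extract, and a somewhat less favourable ICER. If p proves small, showing it protects the conclusion.

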# Research questions, outcomes and data sources

Here and in Appendix A we set out the research questions, outcomes and expected data sources that have been developed in collaboration with the programme's Evaluation Working Group. These support the study overall and will be inputs to the development of the Evaluation Protocol.

They cover four broad areas exploring both positive and negative impacts. Each area is linked to a primary research question and a series of secondary research questions. The areas and their primary research questions are listed below. The full list of research questions and expected data sources are set out in Appendix A.

- 1. Feasibility, acceptability and uptake. Is genomic newborn screening feasible and acceptable and would it be broadly taken up if offered as part of routine care?
- 2. **Test performance and clinical utility.** What is the clinical utility of genomic newborn screening as evidenced by the number of screen-identified diagnoses likely to benefit from intervention compared to standard of care alone?
- 3. Cost effectiveness and positive and negative impacts. What is the cost effectiveness of genomic newborn screening compared to standard of care alone?
- 4. Experiences and attitudes. What are families' and stakeholders' experiences and attitudes to genomic newborn screening?

Questions related to equity will be included and assist in determining any differential areas of positive or negative impact of genomic newborn screening vis-a-vis indices of diversity including ethnicity and socio-economic deprivation.

While it is important to emphasise the breadth of research questions necessary to support policy decisions and therefore explored through the study, we have also identified the following primary and secondary outcomes linked to the areas above and the overarching question of equity.

The primary outcome is:

To determine the clinical utility of genomic newborn screening as evidenced by the number of screen-identified diagnoses likely to benefit from intervention compared to standard of care alone.

The secondary outcomes are:

- To determine the feasibility and acceptability of genomic newborn screening in the NHS utilising mixed-method approaches to assess study implementation.
- To determine the cost effectiveness of genomic newborn screening compared to standard of care alone, supported by a health economic model developed to support the programme.

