Specific costs and utilities are applied to each health state in the three Markov models, therefore patients accrue costs and quality-adjusted life years (QALYs) as they pass through the model. In terms of costs, the model considers treatment costs, direct medical costs, and direct non-medical costs (e.g., social care costs). Utility values for health states are adjusted to account for adverse events from treatments.

Initial data inputs in the model have been obtained from a wide range of sources. The majority of inputs have been sourced from published literature and publicly available datasets. In cases where there was a lack of data available, expert clinicians have been consulted to provide assumptions for the model. For healthcare resource use costs, an analysis of HES datasets has been conducted to obtain resource use inputs for each condition in the model. The model has been built to allow for live data from the Generation Study to be incorporated once available.

Discounting is applied in the model, and differential discount rates are used for costs and benefits. Costs are discounted at a rate of 3.5%, whereas benefits are discounted at a rate of 1.5%.

The key outputs of the model include costs, life years, and QALYs for the blood-spot and WGS arms of the model. These outputs are used to calculate an Incremental Cost Effectiveness Ratio (ICER) to evaluate the cost-effectiveness of introducing WGS screening for newborns. As well as overall costs, QALYs, and ICER estimates, the model also produces disaggregate ICERs for each of the six clusters of diseases in the model. This generates insights into the drivers of cost-effectiveness, particularly useful due to the large variation in treatment costs between the six disease categories.

The model also includes deterministic sensitivity analysis (DSA) to explore the effects of uncertainty on the model's results. As part of the DSA, model inputs are varied between their upper and lower bounds, resulting in a range of plausible results rather than single point estimates. Scenario analyses are also performed, for example on discount rates, to explore the effect of methodological uncertainty within the model.

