# Data analysis

Overview and analysis against the primary study outcome

Data analysis will span the range of research questions and outcomes described above and in Appendix A. As noted above, this will include analysis related to equity across each of the areas to determine any differential positive or negative impact in specific areas or overall linked to diversity including ethnicity and indices of socio-economic deprivation.

Particular and early focus will be given to analysis against the primary study outcome: 'To determine the clinical utility of genomic newborn screening as evidenced by the number of screen-identified diagnoses likely to benefit from intervention compared to standard of care alone'.

As preparation for the study, formal *a priori* sample size estimation was done using a precision approach with the aim to identify the minimum sample size that would ensure a precise estimate of the incidence of diseases.

For the consequent data analysis we will use a Bayesian approach for data modelling outcomes of interest to better account for extreme-values and zero-numerator problems such as in case of rare genetic conditions. We will formulate a prior probability distribution for apparent false positives and false negatives based on the extensive modelling already conducted and also after collecting expert opinions. We will recalculate the posterior probabilities alongside the progression of the programme thus incorporating and refining parameters of uncertainty

Exposition of the data analysis strategy across the full breadth of the research questions and study outcomes is beyond the scope of this protocol.

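### The uncertainty methods named for the ICER are deterministic and attach no probability to its range, and the protocol does not say that the planned posteriors feed it

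*Protocol*

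**What the plan says.** Protocol Section 13 (Research questions, outcomes and data sources) lists cost-effectiveness against standard of care alone among the secondary outcomes, supported by the health economic model.

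The Economic modelling subsection describes a decision tree followed by three Markov models. About 60 conditions are grouped into six clusters. The model holds positive and negative predictive values for both screening tests, "which determine the number of false negatives and false positives in the population". Its costs, life years and QALYs lead to the headline result: "These outputs are used to calculate an Incremental Cost Effectiveness Ratio (ICER) to evaluate the cost-effectiveness of introducing WGS screening for newborns". A separate ICER is produced for each cluster.

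On uncertainty the subsection says: "The model also includes deterministic sensitivity analysis (DSA) to explore the effects of uncertainty on the model's results". It explains that "model inputs are varied between their upper and lower bounds, resulting in a range of plausible results rather than single point estimates". It then adds: "Scenario analyses are also performed, for example on discount rates, to explore the effect of methodological uncertainty within the model".

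The Data analysis subsection of the same section takes a Bayesian approach: "We will formulate a prior probability distribution for apparent false positives and false negatives based on the extensive modelling already conducted", with expert opinion also used. It continues: "We will recalculate the posterior probabilities alongside the progression of the programme".

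**The concern.** A deterministic analysis shows which inputs move the result and how far. It does not show how likely any part of the resulting range is. A decision maker who reads an ICER range that straddles a threshold cannot tell whether the result is probably below it, probably above it, or evenly balanced. The same holds for each cluster ICER, where fewer cases inform the screening inputs.

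The gap stands out because the study plans to hold proper distributions for some of the relevant quantities. Posteriors for false positives and false negatives describe the uncertainty in the model's predictive values. If only upper and lower bounds are taken from them, the information on how likely the values in between are is lost at the step where it would be most useful.

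**Working it through.** The protocol states no ICER, no interval and no input bounds, so there is no figure of its own to reproduce. The check is mainly a comparison of what the text says.

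**1. Methods named.** Economic modelling names a deterministic sensitivity analysis and scenario analyses. No probabilistic sensitivity analysis, input distribution, interval for the ICER or probability of cost-effectiveness appears anywhere in the protocol.

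**2. What those methods return.** If inputs are moved one at a time, the range leaves out joint error. If they are moved together to their bounds, the range shows extreme combinations without saying how unlikely they are. The text does not say which is meant. Neither form carries a probability.

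**3. Where distributions will exist.** Data analysis states priors, later updated, for apparent false positives and false negatives. Economic modelling says that predictive values fix the false results in the model, and that it can take in study data as they arrive. Most of the starting inputs come from the literature and public datasets, with expert assumptions where data are lacking and hospital episode data for resource use. No posterior is described for costs, utilities, efficacy or mortality.

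**4. The link.** No sentence says that the posteriors will be used to express uncertainty in the ICER. No sentence says that they will not.

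**5. Illustration on one input only.** This shows the difference in kind between the ranges. It is not an estimate for the ICER. Inputs:
- prevalence 1/572, range 1/686 to 1/457 (Section 6, Sample size)
- sensitivity 65%, held fixed (Section 6)
- specificity 99% (Section 6), range 98% to 99.5% (Section 10, modelling of variant prioritisation, which used a deliberately over-inclusive gene list and automated output before manual review)

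Formula: PPV = prev × se / [prev × se + (1 − prev)(1 − sp)].

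- Base: (0.65/572) / (0.65/572 + 0.01 × 571/572) = 0.001136 / 0.011119 = 10.2%.
- Prevalence alone: 8.7% to 12.5%.
- Specificity alone: 5.4% to 18.5%.
- Both at their bounds: 4.5% to 22.2%.
- Joint draws (200,000; assumption: independent and uniform over the two ranges): median 8.7%, 95% interval 5.2% to 18.6%.

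The same two inputs give three different ranges. Only the last has a stated probability, and that probability depends on the assumed distributions. Here the joint interval lies close to the range for specificity alone. The example therefore does not show that a deterministic range is always too narrow. It shows that such a range cannot be read as an interval.

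**The case against.** The best defence is that the description is not closed. The text says that the model includes a deterministic analysis, not that nothing else will be done. The decision-tree figure is labelled a draft, and the subsection expects further iteration in response to expert input and best practice. Data analysis says that a full account of the analysis strategy is outside the protocol's scope, and an Evaluation Protocol is to follow. The four evaluation workstreams are described as interlinked and as modelling shared concepts in similar ways.

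Much of this stands, and it rules out several stronger readings that a reader might infer:

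- **That the protocol excludes a probabilistic analysis.** It does not. It names only deterministic methods.
- **That the posteriors will not reach the model.** This would treat silence as a statement, and the wording on live data and linked workstreams leans the other way.
- **That posteriors will exist for all key inputs.** They are stated only for apparent false positives and false negatives.
- **That the ICER's uncertainty is understated by a known amount.** No costs, QALYs or bounds are given. A simple ratio of cost to cases detected would also misrepresent the model, which includes treatment and medical costs that rise with the number of cases found.
- **That national policy would rest on the ICER alone.** Cost-effectiveness is one secondary outcome, and Section 6 calls the primary outcome one of several strands of evidence.

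The defence does not supply the missing analysis. The protocol goes beyond silence: it describes how uncertainty is handled, and what it describes is deterministic. Section 13 (Project Evaluation) also has the sponsor developing the economic model internally, while the Evaluation Partner works on process and impact evaluation, so deferral to the Evaluation Protocol is a weaker answer here than for those workstreams.

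**Conclusion.** The point holds in a limited form. The uncertainty methods named for a secondary outcome give ranges without probability, overall and for each of the six clusters, and the one-way or multi-way form of the deterministic analysis is not stated. The study's planned posteriors bear on the model's predictive values, but their use in the ICER's uncertainty is not specified.

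No numerical size can be put on the effect. The PPV figures above rest on assumed uniform, independent distributions and describe one input before manual review. They must not be carried over to the ICER. This is a worthwhile and inexpensive improvement to the stated method. It does not make the existing deterministic and scenario analyses wrong, since they remain useful for showing what drives the result.

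**What to change.** In Section 13, Economic modelling, add a probabilistic sensitivity analysis:

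- Draw the screening-performance inputs from the study posteriors described under Data analysis, and say so in both places.
- Draw the other inputs (costs, utilities, efficacy, mortality, prevalence weights) from stated distributions.
- Report mean incremental costs and mean incremental QALYs with their joint uncertainty, and give the ICER as the ratio of those two means. Do not average ICERs across draws, because that average is unstable when incremental QALYs come near zero.
- Report the probability of cost-effectiveness across a range of thresholds, since the protocol states none, overall and for each cluster.
- Keep the deterministic and scenario analyses to show drivers, and say whether the deterministic analysis is one-way or multi-way.

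The cost is the modelling time to assign and justify distributions for about 60 conditions and to run the draws. No new data are needed.
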